Study Design: Interested volunteers will be screened by telephone or in person in respective clinics or via televisit and then scheduled for a screening visit (week 0). If potential participants express interest, they will be provided an email address or phone number to call for more information. Alternatively, participants will be asked if they would like to be called to receive more information and are willing to provide their contact information to study staff. If after receiving more information, the potential participant is interested, then pre-screening questions (appendix D) will be asked. If still eligible, then a screening appointment will be arranged by study staff. If the participant is not interested in participating the participant will continue standard OB care for gestational diabetes.

Study visits and intervention: Upon arriving to the pre-intervention visit, informed consent will be obtained after which a point of care HbA1c (if no HbA1c available within the last 2 weeks) will be obtained and oral glucose tolerance test (OGTT) and or HbA1c results reviewed and inclusion/exclusion criteria reviewed. At the pre-intervention session (week 0) the control group will wear CGM for 10 days blinded. The intervention group will be given CGM training and instructions and start Real Time-CGM (RT-CGM). Controls will be asked to follow their OB provider's instructions for checking blood sugar via capillary blood glucose (ie fingersticks). If no recommendations have been given, instructions will be to start checking fingersticks fasting and 1-hour post-meals, which is typical for GDM management. All participants will be asked to write their glucose levels/results in a log provided. RT-CGM participants will be asked to review their RT-CGM and write down their fasting glucose in am, prior to each meal and 1 and 2 hours post-meal. As well they will be instructed to document any sugars < 60 mg/dl seen by CGM in their log.

Participants will then follow-up at week 2 (session 2) at which time the control group will have their blinded CGM data collected and the RT-CGM group will download their CGM data and ensure CGM working appropriately. The control group will continue to monitor fingerstick blood glucose as recommended by their

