pregnancy obstetric provider. The intervention group will continue the RT-CGM device and will be instructed to continue fingersticks only when concerned for hypoglycemia and/or inaccuracy of sensor. The control and intervention groups will follow-up serially for the duration of pregnancy (see schematic for visits below). The control group will wear the blinded CGM at serial timepoints throughout pregnancy and the intervention group will have serial download of RT-CGM. Participants will also have labs checked every 8 weeks which will include HbA1C and fructosamine at beginning and end of the study. It is estimated that participants will be enrolled at 24-28 weeks and have 4 visits (estimating a pregnancy duration of 40 weeks). Some participants may receive a diagnosis of gestational diabetes earlier and thus have more sessions. Maternal and neonatal outcomes will be abstracted from delivery records.

[figure not shown]

Figure 1: Study Design Schematic: N=100 Control N=50 GDM Intevention: GDM N=50

*Approximate Total duration of CGM use would be 14-22

**see timeline for measures appendix B

Figure 2: Timeline for Visits Based on High Risk for Gestational Diabetes and Typical Risk

		Screening Visit 0	Visit 1b High risk	Visit 1a	Visit 2++	Visit 3	Visit 4*
Gestational age Intervention	High Risk	14	20-22 weeks	24-30 weeks	30-32 weeks	34-36 weeks	38-40 Weeks

Gestational age Intervention	Typical Risk	24-28	N/A	24-30 weeks	30-32 weeks	34-36	38-40 Weeks
Gestational age Control	High Risk	14	14-16 weeks	24-30 weeks	30-32	34-36	38-40 Weeks
Gestational age Control	Typical Risk	24-28	N/A	24-30 weeks	30-32 weeks	34-36	38-40 weeks

+++ visits will be a minimum of 2 weeks apart

*38-40 week data only collected in participants that make it to 38- 40 week gestational age

Screening/Pre-Intervention Visit(week 0):

Consent (appendix R) will be obtained prior to any screening procedures being completed, and conducted in a quiet room or private televisit. Participant will be given ample time to ask questions, and a copy of the signed consent form will be given prior to start of screening visit. Participants will fill out a contact form, including emergency contact. Study staff will review medical history and medications, pregnancy history, patient's mother's pregnancy history, sleep history, and lipid profile if available (appendix D), as well as all inclusion/exclusion criteria.

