Week 2 (Visit 1a): Gestational Age 14-16 (Early GDM Dx) or 24-28 weeks (Regular GDM Dx)

RT-CGM and meter will be downloaded for intervention group and meter downloaded for the control group. Glucose logs will be collected. All participants will confirm they have completed RN gestational DM education and nutrition appointments per local standard of care. Vital signs, weight and medications and dose will be recorded at each visit and maternal ultrasound results if available (appendix M).

Week 6 (Visit 1b): Gestational Age 20-22 weeks (Early GDM Dx)

RT-CGM and meter will be downloaded for the intervention group and meter downloaded for the control group. Vital signs, weight and medications and dose will be recorded at each visit and maternal ultrasound results if available (appendix M).

Week 6/Week 14 (Visit 2): Gestational Age 30-32 weeks (Both Early GDM Dx and Regular GDM Dx)

RT-CGM and meter will be downloaded for the intervention group and meter downloaded for the control group. Vital signs, weight and medications and dose will be recorded at each visit and maternal ultrasound results if available (appendix M).

The control group will wear blinded CGM for 10 days and return during regularly scheduled OB visit. The study staff will follow up with participants to remind them to return the devices. If for any reason, the CGM device fails to capture at least 3 days of data, the participants may be asked to repeat this measurement at an unscheduled visit.

Week 10/Week 18 (Visit 3): Gestational Age 34-36 weeks (Both Early GDM Dx and Regular GDM Dx)

RT-CGM and meter will be downloaded for the intervention group and meter downloaded for the control group. Vital signs, weight and medications and dose will be recorded at each visit and maternal ultrasound results if available (appendix M).

Questionnaire on nutrition and exercise in pregnancy and satisfaction with CGM and lifestyle changes with CGM.

The control group will wear blinded CGM for 10 days and return during regularly scheduled OB visit. HgA1c and fructosamine will be collected.

The study staff will follow up with participants to remind them to return the devices. If for any reason, the CGM device fails to capture at least 3 days of data, the participants may be asked to repeat this measurement at an unscheduled visit.

Week 14 /Week 22 (Visit 4) Gestational Age 38- 40 weeks (Both Early GDM Dx and Regular GDM Dx)

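### Figure 2 times the early visits of high-risk women differently by arm and contradicts the visit text: a minor inconsistency that leaves the listed HbA1c and CGM evaluation points untouched

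*Combined protocol and SAP*

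**What the plan says.** Section H describes the early visits in three places.

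- **Narrative (study visits and intervention).** "Participants will then follow-up at week 2 (session 2"): the sentence covers both arms. Controls have their blinded sensor data collected, and "the RT-CGM group will download their CGM data and ensure CGM working appropriately".
- **Visit descriptions.** The first post-baseline visit is headed "Week 2 (Visit 1a): Gestational Age 14-16 (Early GDM Dx) or 24-28 weeks (Regular GDM Dx"). Visit 1b follows at study week 6, at 20-22 weeks, for early diagnoses only. Both entries list downloads for each arm, and both call for vital signs, weight, medications and dose to be recorded.
- **The visit table**, captioned "Figure 2: Timeline for Visits Based on High Risk for Gestational Diabetes and Typical Risk". In the high-risk rows, Visit 1b is at 20-22 weeks for RT-CGM and 14-16 weeks for controls. Visit 1a is at 24-30 weeks in both arms. The typical-risk rows are the same in both arms.

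A footnote to Figure 2 adds that "visits will be a minimum of 2 weeks apart". It is marked with three plus signs, while the only matching column heading (Visit 2) carries two, so its scope is unclear.

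The early group is a subset: "Some participants may receive a diagnosis of gestational diabetes earlier and thus have more sessions". Section H expects enrolment at 24-28 weeks, and the number of early diagnoses is not given.

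**The concern.** Figure 2 and the visit text cannot both be followed for early-GDM women, and nothing visible says which prevails. The control cell for Visit 1b equals the window that the visit text gives to Visit 1a, which suggests that the two labels were confused when the table was made.

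If staff work from the table, the schedule depends on the randomized arm. RT-CGM women who enter at 14 weeks lose the week-2 check that the sensor works. That check has a purpose: these women are told to use fingersticks only if they suspect a low or doubt the sensor, and the log that their OB provider sees holds CGM values. Controls lose the 20-22 week visit. Interim weight, vital signs and medication dose are then taken at different gestational ages in the two arms.

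**Working it through.** The plan states no figure on this point, so there is none to reproduce. The check sets the schedules side by side and then does the week arithmetic.

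| Early-GDM visit | Figure 2, RT-CGM | Figure 2, control | Visit text, both arms |
|---|---|---|---|
| Screening | 14 | 14 | study week 0 |
| Visit 1a | 24-30 | 24-30 | study week 2, 14-16 |
| Visit 1b | 20-22 | 14-16 | study week 6, 20-22 |
| Visit 2 | 30-32 | 30-32 | 30-32 |
| Visit 3 | 34-36 | 34-36 | 34-36 |
| Visit 4 | 38-40 | 38-40 | 38-40 |

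Figures are weeks of gestation unless marked as study weeks. All four rows of Figure 2 have the same number of cells, so a fault in the text extraction is unlikely.

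**Input.** Entry at 14 weeks, the only high-risk entry age in Figure 2; Section F excludes anything earlier. Interval = gestational age at visit minus gestational age at entry.

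**Figure 2, entry at 14 weeks**

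- First RT-CGM visit: 20 − 14 = 6 to 22 − 14 = 8 weeks after entry.
- First control visit: 14 − 14 = 0 to 16 − 14 = 2 weeks after entry.
- Arm difference in Visit 1b: 20 − 16 = 4 to 22 − 14 = 8 weeks.
- Control wait until the 24-30 week visit: 24 − 16 = 8 to 30 − 14 = 16 weeks.

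**If the two-week footnote covers every visit.** The control Visit 1b must be at 14 + 2 = 16 weeks. The arm difference becomes 20 − 16 = 4 to 22 − 16 = 6 weeks, and the control wait 24 − 16 = 8 to 30 − 16 = 14 weeks.

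**Visit text, entry at 14 weeks.** Visit 1a is at 14 + 2 = 16 weeks and Visit 1b at 14 + 6 = 20 weeks in both arms. Both fall inside the stated windows, and the arm difference is 0.

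**Later entry under Figure 2**

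- Entry at 16: the first RT-CGM visit is 20 − 16 = 4 to 22 − 16 = 6 weeks after entry.
- Entry at 18 to 20: study week 2 falls at 18 + 2 = 20 to 20 + 2 = 22 weeks, inside the RT-CGM Visit 1b window, so the check need not be missed.
- Controls entering after 16 weeks: the 14-16 week cell has already passed, so the table cannot be followed literally.

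**What depends on Visits 1a and 1b**

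- Section K lists HbA1c at baseline, 30-32 and 34-36 weeks, fructosamine at baseline and 34-36 weeks, and questionnaires at baseline and 34-36 weeks.
- Section N on glucose and CGM data evaluates RT-CGM at baseline and Visits 2-4, and blinded CGM at baseline and Visits 2 and 3.
- None of these points is Visit 1a or 1b. Sections E and H also describe HbA1c as eight-weekly, but the descriptions of Visits 1a and 1b include no blood draw, so the dated list in Section K is used here.

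**The case against.** The strongest reply is that this is a clerical slip in a summary table. The narrative and the visit descriptions agree with each other, carry more detail, and bring both arms back at week 2. Every consequence requires staff to prefer the table. Figure 1 ("Figure 1: Study Design Schematic: N=100 Control N=50 GDM Intevention: GDM N=50") and the appendix named in its note ("see timeline for measures appendix B") are not visible, and either may already settle the matter. This stands, and it is why the point is minor. It does not remove the conflict, because Figure 2 is itself an operational timeline.

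The missed check is also partly covered. Data from phone users can be downloaded remotely, telephone support is offered, and each RT-CGM woman has a back-up meter. That helps, but receiver-only users are downloaded at visits, and none of these is a scheduled check.

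One could defend arm-specific timing on the ground that controls must return a blinded sensor after 10 days. The narrative, however, places that collection and the RT-CGM check at the same week-2 visit, and the typical-risk rows draw no such distinction.

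A reader might infer more than the documents support:

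- **That the glycemic comparison is distorted.** The listed evaluation points do not use Visits 1a or 1b, and the later windows match between arms.
- **That Aim 5 is biased.** Dose is recorded at these visits, so an effect on cumulative insulin dose is possible. But no visible text says how the dose is summed, and the insulin-use form is not visible.
- **That every early-GDM woman on RT-CGM loses the check.** That follows for entry at 14 weeks, not for entry at 18-20.

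**Conclusion.** Figure 2 is wrong as written for high-risk women: a minor internal inconsistency. It gives the arms different Visit 1b windows and moves Visit 1a to 24-30 weeks in both, against text that gives both arms study weeks 2 and 6.

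The size holds only if staff follow the table, and is largest for entry at 14 weeks: no scheduled RT-CGM visit for 6-8 weeks, no 20-22 week control visit, and interim records 4-8 weeks apart by arm (4-6 if the footnote covers all visits). The number of women affected is not stated. No consequence for the listed HbA1c, fructosamine, questionnaire or CGM evaluation points is shown; that conclusion rests on the dated lists in Sections K and N and on the unseen Figure 1 and Appendix B not adding to them.

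**What to change.** Make the two high-risk rows of Figure 2 identical and consistent with the visit descriptions: Visit 1a at study week 2 and Visit 1b at study week 6, counted from entry, in both arms. For entry at 14 weeks these are the 14-16 and 20-22 week windows. Counting from entry matters because the 14-16 week window does not fit later starts (15 + 2 = 17). Leave Visits 2-4 unchanged, and check that Figure 1 and Appendix B agree.

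The cost is two corrected table rows. Figure 2 and the visit text each already have two early-GDM visits between screening and Visit 2, so no visit is added.

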Oct 18 2024

Clinicaltrials: Study 00011755

INVESTIGATOR-SPONSORED STUDY

The Use of Real-Time Continuous Glucose Monitoring (RT-CGM) in Gestational Diabetes

[name], [name], [name].

Division of Metabolism, Endocrinology and Nutrition

**Department of Medicine
University of Washington
[name]
[name]
[name]**

Correspondence to:

**[name]
Assistant Professor
Email: [contact]
[contact]**

Table of Contents

A. Specific Aims/ Hypothesis.....	4
B. Background.....	4
C. Significance:	4
D. Research Recruitment and Population.....	5
E. Statistical Considerations.....	6
F. Inclusion/Exclusion Criteria.....	7
G. Diagnosis of GDM.....	8
H. Study Design.....	9
I. Randomization.....	12
J. Study Procedures, Materials and Devices.....	13
K. Measurements.....	14
L. Collection of Human Biological Specimens.....	15
M. Questionnaires.....	16
N. Glucose/CGM Data /Evaluation Measures.....	17
O. Antenatal Ultrasound Markers.....	17

P. Risks and Side-Effects.....	17
Q. Benefits.....	18
R. Conflict of Interest.....	18
S. Confidentiality.....	18
T. Compensation.....	19
U. Appendixes.....	19

RESEARCH PROTOCOL

TITLE: A Study on the Use of Real-Time Continuous Glucose Monitoring (RT-CGM) in Gestational Diabetes

A. Specific Aims/ Hypothesis: We hypothesize that use RT-CGM in those with gestational diabetes will improve/ reduce glycemic variability in pregnancy and potentially improve fetal and maternal outcomes.

Aim 1. Evaluate if Real Time Continuous Glucose Monitoring improves mean glucose, time in range, time above and below range, mean amplitude of glycemic excursions (MAGES) and standard deviation of blood sugars and coefficient of variation (CV)

Aim 2. Evaluate if improved glycemic variability improves fetal and maternal outcomes in pregnancies affected by gestational diabetes.

Aim 3: Evaluate participants' perception of RT-CGM use in pregnancies affected by gestational diabetes.

Aim 4: Evaluate nutritional and lifestyle changes in GDM and pregnancy and effect of RT-CGM

Aim 5: Evaluate if RT-CGM decreases need for initiation of oral diabetes medication and/or insulin. If insulin initiated, evaluate if RT-CGM reduces cumulative insulin dose.

Aim 6: Evaluate nocturnal hypoglycemia in pregnancy and if RT- CGM lessens nocturnal hypoglycemia

B. Background and Significance

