Vital signs will be collected, including height, weight (current and pre-pregnancy), blood pressure, maternal resting heart rate, and estimated gestational age. Maternal ultrasound results will be reviewed if available.

Glucose tolerance test results will be reviewed. Two blood pressure and pulse readings will be taken and HbA1c, both point of care (fingerstick) and HbA1c serum and fructosamine via LabCorp will be obtained. Approximately 1 teaspoon of blood will be drawn. If a patient has an HbA1c documented in the medical record within 2 weeks of the pre-intervention session, then the point of care HbA1c will not be done. The available HbA1c will be used. If they meet all inclusion and exclusion criteria (as outlined above), they will be randomized into either the RT-CGM intervention or control arm at the screening visit.

At the pre-intervention session (week 0) the control GDM group will be asked to wear the CGM blinded for 10 days. They will be asked to continue their usual diet and activity. If, for any reason, the CGM device fails to capture at least 3 days worth of data, the subject may be asked to repeat this measurement at an unscheduled visit. The control group will be given a glucose meter (onetouch) and instructed to follow their obstetric provider's recommendations about checking glucose by meter or if they have not been given instructions or do not remember their instructions they will be asked to check sugars fasting and 1 hour after meals. They will also be given a handout that explains glucose goals and how food and activity effects glucose levels. (Appendix A1,A2). The intervention group will be given RT-CGM and instructed on use with a handout that explains glucose goals and how food and activity effects glucose levels (see handout/Appendix A). The intervention group will also be given a glucose meter (onetouch) and instructed to use for symptoms of low glucose or if they question the accuracy of the CGM. Both groups will be given standard gestational diabetes teaching and nutrition counseling by the RN in clinic and with individual nutrition appointments with the nutritionist, as per current local standard of care.

Participants will be given self-report questionnaires on physical activity, nutrition, sleep history, pregnancy history and overall wellness. Week 0 consenting and baseline data/measurements will take between 1 hour 30 minutes and 2 hours.

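### At week 0, after randomisation, only the control arm is asked to keep its usual diet and activity, and the request conflicts with the counselling and handout given to the same women

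*Combined protocol and SAP*

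**What the plan says.** Section H (Screening/Pre-Intervention Visit) randomises eligible women at the screening visit. The next paragraph opens with the control arm, who are to wear the CGM "blinded for 10 days. They will be asked to continue their usual diet and activity". The only group named up to that point in the paragraph is the control group, so the request is addressed to controls.

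For the intervention arm the paragraph says they are "given RT-CGM and instructed on use with a handout that explains glucose goals and how food and activity effects glucose levels". Neither this paragraph nor any other part of the document asks that arm to keep its usual diet and activity.

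The same paragraph says of controls: "They will also be given a handout that explains glucose goals and how food and activity effects glucose levels". It then says "Both groups will be given standard gestational diabetes teaching and nutrition counseling by the RN in clinic", and adds individual nutritionist appointments. At week 2, "All participants will confirm they have completed RN gestational DM education and nutrition appointments per local standard of care".

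Aim 4 in Section A is to "Evaluate nutritional and lifestyle changes in GDM and pregnancy and effect of RT-CGM".

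**The concern.** A request to hold lifestyle constant suits a run-in that all participants share before allocation. Here it comes after allocation and reaches one arm. If controls follow it, the arms differ in the first days by a lifestyle instruction as well as by access to real-time readings.

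Two uses of the data are exposed. The first is any comparison of CGM measures over weeks 0-2, where a control-only request not to change could make RT-CGM look better. The second is the controls' first blinded wear, which Section N treats as their baseline CGM and which can enter the mixed models of CGM readings planned in Section E. In an analysis of change from that baseline the bias could run the other way: the controls' starting point is held at usual lifestyle, while the RT-CGM arm's first window is already on treatment.

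There is also a delivery problem. The same woman is asked to carry on as usual and is taught, at the same visit, how food and activity move her glucose. Staff may resolve that conflict differently from one participant to the next.

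**Working it through.** The protocol gives no figure on this point, so there is none to reproduce. The check compares the week-0 instructions by arm and then works out how much follow-up 10 days represents.

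**Week-0 instructions by arm (Sections H and J)**

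| Item | Control | RT-CGM |
|---|---|---|
| CGM | Blinded, 10 days | Real-time, from week 0 |
| Request to keep usual diet and activity | Yes | None found |
| Handout on glucose goals, food and activity | Yes (adapted to fingersticks) | Yes |
| GDM teaching and nutrition counselling | Yes | Yes |
| Completion of counselling confirmed at week 2 | Yes | Yes |

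The CGM row is the intended contrast. The request to keep usual diet and activity is the only lifestyle instruction in the table that differs by arm. It also conflicts with the handout and counselling rows for the same women.

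**Reach within the CGM data.** Section J places the controls' blinded wears at the beginning, at 30-32 weeks and at 34-36 weeks. The request appears only with the first, so it covers all of one window out of three.

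**Share of the time to the first follow-up HbA1c** (30-32 weeks, Section K). Share = 10 days / days from week 0 to that visit.

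- Enrolment at 14 weeks: 30 - 14 = 16 weeks = 112 days, and 32 - 14 = 18 weeks = 126 days. 10/112 = 8.9%; 10/126 = 7.9%. Section H also labels this visit week 14 for early diagnosis, which gives 10/98 = 10.2%.
- Regular diagnosis, with Visit 2 labelled week 6 in Section H: 10/42 = 23.8%.
- Upper limit: Visit 1a is at week 2 (Section H), and the note to Figure 2 sets at least 2 weeks between visits. Visit 2 therefore falls no earlier than day 14 + 14 = 28. 10/28 = 35.7%.

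Section L describes HbA1c as reflecting about 3 months. Against roughly 90 days, 10 days is 10/90 = 11%. All of these are shares of time. None is an estimate of bias in glucose or HbA1c.

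**Aim 4.** Diet and activity questionnaires are taken at baseline and at 34-36 weeks (Section K). The shortest gap is enrolment at 30 weeks with the questionnaire at 34 weeks, which is 28 days. The activity instrument covers the last 7 days (Section M), so its recall runs over about days 21-28, after a 10-day request would have ended. The protocol gives no recall period for the nutrition instrument.

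**The case against.** The best defence is that the same paragraph limits the asymmetry. Both arms receive a food-and-activity handout, the same GDM teaching and the same nutrition counselling, and completion is checked in everyone. The sentence may mean only that controls should not behave differently because they are wearing a sensor. It is not repeated at the later blinded wears. The first window is in any case non-comparable for a larger reason, because it is blinded in one arm and real-time in the other, and rewording one sentence does not change that.

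Most of this stands and lowers the severity. It does not remove the point. The shared counselling is what makes the control request contradictory. The milder meaning is possible, but the text does not state it, and handouts A1 and A2 are not available to settle it.

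A reader might go further in three ways that the documents do not support.

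- *Aim 4 is compromised.* On a 10-day reading this is not shown, because the follow-up questionnaires come weeks later and nothing in the documents establishes a carry-over.
- *The 10 days could fill most of the time to the first follow-up HbA1c.* Taking enrolment at 28 weeks and the visit at 30 weeks gives 10/14 = 71%, but the week-2 visit and the two-week spacing rule that out.
- *This is confounding.* The difference arises after randomisation and is part of how the arms are handled, so performance bias from a differential co-intervention is the accurate description.

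**Conclusion.** The one-arm request and its conflict with the counselling are both in the text. Followed as written, the request adds a differential co-intervention to the week 0-2 CGM contrast and to the controls' baseline window. The direction of bias depends on whether the analysis compares early levels or change from baseline, and its size cannot be estimated from the documents. The exposure is one of three blinded windows. The 10 days are about 8-9% of the time to the 30-32-week HbA1c for enrolment at 14 weeks, 24% on the week-6 schedule and at most about 36%.

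This rests on two assumptions: that the request lasts as long as the 10-day wear it follows, and that Visit 1a takes place at week 2. The first is an inference, since the sentence has no end date. If the request is open-ended, it bears directly on Aim 4 and on later glycaemia, and the point becomes more serious. Severity is minor to moderate. It should be corrected, but on the 10-day reading it does not undermine the trial's main comparisons.

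**What to change.** Reconcile the statements in Section H so that any diet-and-activity instruction at week 0 is the same for both arms, or is given to neither. State how long it lasts and how it fits with the handout and the nutrition counselling, and bring handouts A1 and A2 into line. The clinical content is for the investigators to settle. Arm-specific instructions on CGM use and fingersticks are the intervention contrast and stay as they are.

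If women have already been enrolled under the current text, record what each arm was actually told and interpret the first CGM window accordingly.

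The cost is about one amended sentence and a check of two handouts, with no added visits, data or participants.
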